Urinalysis ^{n,o}	X	X			X		X							
Urine for drugs of abuse ^p	X													
Study drug administration ^q		X												
Blood samples for PK analysis ^r		X	X	X	X	X	X	X	X	X	X	X	X	X
Blood samples for immunogenicity analysis ^s		X					X	X	X	X	X	X	X	X
Blood sample for quantitative HBsAg	X	X	X	X	X	X	X	X	X	X	X	X	X	X
Blood sample for anti-HBs	X				X		X	X	X	X	X	X	X	X
Blood sample for HBeAg qualitative	X								X ^t					X ^t
Blood sample for HBeAg quantitative ^t		X						X	X					X
Blood sample for anti-HBe		X							X					X
Blood sample for HBV RNA quantitation and HBcrAg quantitation		X						X	X	X		X	X	X

Part B, C, and D															
Study Stage	Screening	Dosing Day ^a	Post-dose Follow-up Period							Extended Follow-up Period ^b					
Study Visit Week					W1		W2	W4	W8/ET ^c	W12	W16	W24	W32	W40 / EF ^d	
Study Visit Day±Visit Window	D -42 to -1	D1 ^e	D2	D4+1	D8±1	D11±1	D15±2	D29±2	D57±7	D85 ±7	D113 ±7	D169 ±7	D225 ±7	D281 ±7	
Blood sample for HBV DNA quantitation ^u	X	X	X ^v	X ^v	X	X ^v	X	X	X	X	X ^v	X	X ^v	X	
Blood sample for analysis of peripheral immune responses ^w		X			X		X	X	X	X		X		X	
Blood sample for RNA Paxgene tube ^x		X			X		X	X	X	X		X		X	
HBV resistance surveillance ^{u,y}		X			X		X	X	X	X	X	X	X	X	
Blood sample for Fc gamma receptor genotyping and for immunoglobulin allotyping		X													
CCI															
Local tolerability ^{aa}		X	X	X	X										
Review/record AEs ^{bb}	X									X					
Concomitant medications								X							
NRTI medication adherence ^{cc}								X							

AE = adverse event; ECG = electrocardiogram; EF = end of follow-up; ET = end of treatment; HBcrAg = hepatitis B core-related antigen; HBeAg = hepatitis B e-antigen; HBsAg = hepatitis B surface antigen; HBV = Hepatitis B Virus; NRTI = nucleoside/nucleotide reverse transcriptase inhibitor; PK = pharmacokinetic; SAD = single ascending dose

Note: When scheduled at the same timepoints, the assessments of vital signs and 12-lead ECGs must be performed before the blood sample collections.

- ^a Subjects may be admitted to the clinical investigative site on Day -1 or 1 and discharged after all study assessments are performed on Day 1. Patients must be monitored through at least 6 hours post-dose prior to discharge.

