Visit Windows: The analysis visit windowing rules for protocol-defined visits are provided in Appendix 2.

Incomplete/Missing data: In general, missing data will not be imputed, unless specified otherwise.

For virology tests and safety laboratory parameters, the following rules will be applied in calculation of summary statistics and absolute change from baseline values:

- If a data point is missing by reported as “< lower limit of quantification (LLOQ) or < limit of detection (LOD)” with “Target Not Detected (TND)” or reported as the meaning of “Not Detected”, then the missing data point will be imputed as zero.
- If a data point is missing by reported as “< LLOQ or < LOD” with “Target Detected (TD)”, then the missing data point will be imputed as the half of LLOQ value or 1 unit less than the LOD value, respectively. For example, if the LOD values are 0.5 and 0.03, then the imputed values will be 0.4 and 0.02. When the LOD value is 1, it will be imputed as 0.9.

- If a data point is missing by reported as “< LLOQ or < LOD” without knowing “TD or TND”, then the missing data point will be treated as “< LLOQ, TD or < LOD, TND”.
- If a data point is missing by reported as “> upper limit of quantification (ULOQ)” without knowing “ULOQ”, then the missing data point will be imputed as 1 unit greater than the value of ULOQ.
- If a data point is missing by reported as the meaning of “no results obtained”, then it is considered as the missing data and not included in data summary and analysis.

Logarithm transformation will be used for analysis of virological variables. For the \log_{10} transformed data using LOD value, 1) a missing data point due to untransformed value of zero will be imputed as zero, when $\text{LOD} > 1$; and 2) a missing data point due to untransformed value of zero will be imputed as \log_{10} (1 unit less than LOD value), when $\text{LOD} < 1$.

The reported value will be used in individual subject listings for all virology tests and safety laboratory parameters.

Outliers: No formal statistical analyses will be performed to detect and/or remedy the presence of statistical outliers.

Repeated Observations: Measurements recorded at different time points are defined as repeated observations. If an assessment has planned repeated measurements, then statistical summaries will present all planned time points, as appropriate.

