Notes: 
¹ Visit name for analysis purpose is used to report data in tables and figures.
 
² The analysis visit windows will be applied using the following rules for both scheduled and unscheduled visits:
 
 a. If no numerical measurement is available within a visit window, the measurement will be considered missing for the visit. b. If there is more than 1 numerical measurement available within a visit window, use the following rules: 
 i. If the scheduled visit measurement will be used if it is available ii. If not, the unscheduled visit measurement closest to the target day will be used; or iii. If there are multiple unscheduled visit measurements with the same distance from the target day, the latest measurement will be used. 
³ For an assessment, e.g., laboratory, ECG and vital sign measurement collected on the date of first dose of study drug, if it cannot be determined whether the measurement is before or after the first dose:
 
 a. Scheduled measurement will be treated as pre-dose observation. b. Unscheduled measurement will be treated as post-dose observation. 
⁴ For vital signs, Day 1 will be included in the Day 1 visit window to account for the post-dose assessments on Day 1, .
 
⁵ PK analysis window will follow the protocol-defined assessment visit window.
			

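### For HBsAg and Part D HBV DNA, the SAP's analysis windows put a protocol-compliant Week 2 sample taken on Day 13 into the Day 11 visit, which leaves Week 2 empty

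*SAP*

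**What the plan says.** SAP Section 6.1 hands visit assignment to an appendix: "The analysis visit windowing rules for protocol-defined visits are provided in Appendix 2". Table 7-1 there defines half-open windows in study days. For HBsAg and for HBV DNA in Part D, the Day 11 visit is (9, 13] and Week 2 is (13, 22].

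The notes to Table 7-1 say how the windows work. Assignment is by study day for every sample: "The analysis visit windows will be applied using the following rules for both scheduled and unscheduled visits". An empty window is dealt with in note 2a: "If no numerical measurement is available within a visit window, the measurement will be considered missing for the visit". Note 2b covers windows with more than one value, in three steps: "If the scheduled visit measurement will be used if it is available"; "If not, the unscheduled visit measurement closest to the target day will be used"; "If there are multiple unscheduled visit measurements with the same distance from the target day, the latest measurement will be used".

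Protocol Appendix 3, the schedule for Parts B, C and D, allows the Day 11 visit within 1 day and the Week 2 visit (target Day 15) within 2 days of target. Its row headed "Blood sample for quantitative HBsAg" is marked at both visits. So is the row headed "Blood sample for HBV DNA quantitation"; its Day 11 entry carries a footnote that is partly blacked out, but Table 7-1 itself provides a Day 11 window for HBV DNA in Part D.

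**The concern.** The two documents disagree about Day 13. The protocol treats it as a valid Week 2 day and not as a valid Day 11 day. The SAP treats it as Day 11. A site that keeps to the protocol can therefore have its Week 2 HBsAg sample reported under another visit.

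Two consequences follow. The subject drops out of the Week 2 row. The Day 11 row either receives a Day 13 value in place of a missed visit, or has two scheduled candidates that note 2b does not rank.

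The SAP is also inconsistent within Table 7-1. The Week 2 window is (11, 22] for the Parts B, C and D chemistry, liver tests, hematology, coagulation and vital signs, and for anti-HBs. Note 5 keeps PK samples on the protocol's own visit windows. From a single Day 13 visit, ALT, anti-HBs and the PK sample would be labelled Week 2 and HBsAg would be labelled Day 11.

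SAP Section 6.7.2 summarizes HBsAg and Part D HBV DNA, with change from baseline, at each visit to Week 8 and plots the mean changes. Each cohort is planned with six active subjects and two on placebo (protocol Section 5.3), so one displaced subject is a visible share of a row.

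**Working it through.** **Inputs.** Permitted visit days come from protocol Appendix 3. Analysis windows for HBsAg and Part D HBV DNA come from SAP Table 7-1.

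| Visit | Permitted days | SAP window | All permitted days inside? |
|---|---|---|---|
| Day 2 | 2 | [1, 2] | yes |
| Day 4 | 4–5 | (2, 6] | yes |
| Week 1 | 7–9 | (6, 9] | yes |
| Day 11 | 10–12 | (9, 13] | yes |
| Week 2 | 13–17 | (13, 22] | **no: Day 13 falls in Day 11** |
| Week 4 | 27–31 | (22, 43] | yes |
| Week 8 | 50–64 | (43, 64], reading the upper limit as Day 64 | yes |

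**Where the boundary comes from.** The midpoint of target Days 11 and 15 is (11 + 15)/2 = 13, and that of Days 15 and 29 is (15 + 29)/2 = 22. The SAP's limits are these midpoints, with a tie going to the earlier visit. Day 13 is 2 days from each target, so closeness to target does not favour either visit; the protocol window does.

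**Other window sets.** The same check on the Parts B, C and D safety-laboratory windows, the anti-HBs windows, the main extended follow-up windows and the main Part A windows found no mismatch. The problem is one day in one block of the table.

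**Applying the notes to a Week 2 sample on Day 13.**

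- Day 11 visit made on Days 10–12: (9, 13] holds two scheduled values. Note 2b prefers scheduled to unscheduled and then ranks unscheduled values only, so no step chooses between the two.
- Day 11 visit missed: the Week 2 sample is reported as Day 11.
- In both cases (13, 22] holds no scheduled value, and Week 2 is missing under note 2a unless an unscheduled sample falls on Days 14–22.

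**Size.** One of five permitted days is affected. Let q be the share of Week 2 visits that fall on Day 13; the documents do not give it, so a range is assumed. For six active subjects, P(at least one affected) = 1 − (1 − q)^6:

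- q = 0.05: 1 − 0.95^6 = 0.26
- q = 0.10: 1 − 0.90^6 = 0.47
- q = 0.20: 1 − 0.80^6 = 0.74

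SAP Table 2 marks nine HBV cohorts as enrolled (four in Part B, three in Part C, two in Part D). At six active each that is 54 subjects. The chance of at least one affected active subject is 1 − 0.99^54 = 0.42 at q = 0.01 and 1 − 0.95^54 = 0.94 at q = 0.05.

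If one of six subjects is lost from the Week 2 mean, the mean shifts by a random amount with SD = s × √(1/5 − 1/6) = 0.183 s, where s is the between-subject SD. At an assumed s of 0.5 log10 this is 0.09 log10.

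**With the boundary at Day 12.** Using (9, 12] and (12, 22], Days 10–12 map to Day 11 and Days 13–17 map to Week 2. The check then shows no mismatches.

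**The case against.** The boundary fact is not disputable; the case against concerns its weight.

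- **The endpoint is untouched.** The secondary endpoint is the maximum reduction in HBsAg (and maximum change in HBV DNA in Part D). It is taken at nadir over follow-up to Week 8 and does not depend on these windows. This stands, and it limits the effect to by-visit tables and plots in a study with no formal hypotheses. The sample also stays in the listings.
- **The frequency is unknown.** One day in five is a count of calendar days, not a rate. Day 15 falls on the same weekday as dosing, so a Day 13 visit means coming two days early, 1 to 3 days after a compliant Day 11 visit. After a Monday or Tuesday dose, Day 13 is a weekend. This stands: the probabilities are illustrative, and the 20% case may well be too high.
- **The shift has no direction.** Losing a subject costs precision, and no bias has been shown. This also stands.
- **Note 2b could be read to choose.** The scheduled measurement might mean the one from the like-named visit, which would select the Day 11 sample. The text does not say so, and under that reading the Day 13 value is used nowhere by visit and Week 2 is still empty.
- **Different labels for ALT and HBsAg may not matter.** The SAP shows no analysis that pairs them by visit. That is fair, so the label difference is evidence of inconsistency and not a separate harm.

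**Conclusion.** The concern holds. As written, Table 7-1 moves an on-schedule HBsAg or Part D HBV DNA sample out of its own visit when Week 2 is done on Day 13, and the notes do not bring it back. The extent is one of five permitted Week 2 days, for two measurements, in by-visit summaries and plots only.

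The number of subjects affected cannot be known from the documents. The cohort probabilities rest on assumed Day 13 rates and six active subjects per cohort, and the 0.09 log10 figure rests on an assumed SD. The finding itself needs none of these assumptions, because it follows from the two sets of windows. It should be corrected, but it does not threaten the primary safety analysis or the nadir endpoint.

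**What to change.** In SAP Table 7-1, in the block for HBsAg and HBV DNA (Part D), change Day 11 from (9, 13] to (9, 12] and Week 2 from (13, 22] to (12, 22]. Every permitted visit day then falls in its own analysis visit. Day 13 also carries the Week 2 label, as it already does for safety laboratory tests, anti-HBs and PK.

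The boundary change does not settle two scheduled values in one window when a visit is made outside its protocol window. One added line in note 2b would close that gap, for example by taking the scheduled value from the visit of the same name.

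The cost is one boundary value, entered in two cells of one table, and optionally one sentence. No new data are needed. SAP Section 1 has the plan finalized before the final database lock and provides for amendments, so the change fits the existing process.

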10.2. Data Handling Conventions

Laboratory data that are continuous in nature but are less than the LLOQ or above the upper limit of quantitation will be imputed to the value of the lower or upper limit minus or plus 1 significant digit, respectively (e.g., if the result of a continuous laboratory test is < 30, a value of 29 will be assigned; if the result of a continuous laboratory test is < 30.0, a value of 29.9 will be assigned).

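### SAP 6.1 replaces the protocol's below-limit imputation rule without declaring it, and its log10 handling of Not Detected results is not coherent

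*SAP*

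**What the plan says.** Protocol 10.2 has one convention for continuous laboratory data outside the quantitation limits: the result "will be imputed to the value of the lower or upper limit minus or plus 1 significant digit, respectively". Its example is explicit: "if the result of a continuous laboratory test is < 30, a value of 29 will be assigned". It makes no distinction between Detected and Not Detected, and nothing in it confines the rule to safety laboratory tests.

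SAP 6.1 covers the same kind of data: "For virology tests and safety laboratory parameters, the following rules will be applied". A result below the LLOQ or LOD that is Not Detected is treated this way: "then the missing data point will be imputed as zero". For a Detected result, "the missing data point will be imputed as the half of LLOQ value or 1 unit less than the LOD value", the first for results below the LLOQ and the second for results below the LOD. The SAP's examples are: "if the LOD values are 0.5 and 0.03, then the imputed values will be 0.4 and 0.02"; an LOD of 1 becomes 0.9. If target status is unknown, a result below the LLOQ is treated as Detected and a result below the LOD as Not Detected.

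Virological variables are analysed on the log scale. For log10 data that use the LOD, SAP 6.1 says that "a missing data point due to untransformed value of zero will be imputed as zero" when the LOD is above 1. When the LOD is below 1, the log value is log10 of the LOD minus one unit.

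SAP 6.7.2 summarises the change from baseline at nadir, up to Week 8, for HBsAg (Parts B, C and D) and HBV DNA (Part D). These are the secondary endpoints of maximum HBsAg reduction and maximum HBV DNA change. SAP 6.8.1 lists five changes to the protocol: four concern analysis sets and one the TEAE definition. None concerns below-limit values.

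**The concern.** A nadir picks out the lowest value, so in any subject who falls below an assay limit the imputed number is the endpoint. That makes the convention part of the endpoint definition for the best responders. Two things then matter. First, the SAP's convention differs from the protocol's, and a reader who relies on 6.8.1 would not know. Second, a below-limit rule should keep Not Detected at or below Detected, and should give a result the same meaning on the raw and log scales. The SAP's rule does not guarantee either, so two programmers could derive different nadirs from the same data, and under some limits a deeper response would be scored as a smaller one.

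**Working it through.** **Inputs.** The rules and worked examples come from protocol 10.2 and SAP 6.1. Part D entry requires HBV DNA of at least 1,000 IU/mL at screening (protocol 6.4). Each cohort has 6 active subjects (protocol 5.3). No assay LLOQ or LOD is given, so every limit below is an assumption unless it is one of the documents' own examples.

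**Reproducing the documents' figures.** Reading one unit as 1 in the last reported digit gives 30 → 29 and 30.0 → 29.9 (protocol), and 0.5 → 0.4 and 0.03 → 0.02 (SAP). The SAP states 1 → 0.9 as an explicit exception.

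**1. Conflict with the protocol.** For a result of <30, protocol 10.2 gives 29 (log10 = 1.46). The SAP gives 30/2 = 15 (1.18) if it is below the LLOQ and Detected. If Not Detected, it gives 0 on the raw scale and 0 on the log scale. The SAP's LOD-minus-one-unit clause has the same form as 10.2; the conflict lies in LLOQ/2 and in zero for Not Detected.

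**2. Raw against log scale.** Not Detected is always 0 on the raw scale. On the log scale it stands for 10^0 = 1 IU/mL when the LOD is above 1, and for the LOD minus one unit when it is below 1 (0.02 for the SAP's LOD of 0.03). Neither case covers LOD = 1.

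**3. Order of Detected and Not Detected.** Suppose an assay reports against both limits and the log rule is applied to its zeros. With LOD < 1, Not Detected ranks above Detected when LOD − 1 unit > LLOQ/2.

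| Assumed LLOQ | Assumed LOD | Detected, log10(LLOQ/2) | Not Detected, log10(LOD − 1 unit) | Reversed? |
|---|---|---|---|---|
| 0.05 | 0.05 | log10(0.025) = -1.60 | log10(0.04) = -1.40 | yes |
| 0.05 | 0.04 | -1.60 | log10(0.03) = -1.52 | yes |
| 0.05 | 0.03 | -1.60 | log10(0.02) = -1.70 | no |
| 0.05 | 0.02 | -1.60 | log10(0.01) = -2.00 | no |

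For the SAP's own LODs, reversal needs an LLOQ below 2 × 0.4 = 0.8 (LOD 0.5) or below 2 × 0.02 = 0.04 (LOD 0.03). In the first row, a subject with one Detected and one Not Detected visit has the raw nadir at the Not Detected visit (0) and the log nadir at the Detected visit (-1.60). For HBV DNA with an LLOQ of at least 2 and an LOD above 1 there is no reversal, because LLOQ/2 is then at least 1.

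**4. Part D HBV DNA against protocol 10.2.** With LOD > 1, the extra reduction is log10(limit − 1) − 0 for Not Detected and log10(limit − 1) − log10(limit/2) for Detected.

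| Assumed limit (IU/mL) | Protocol 10.2 | SAP Detected (extra) | SAP Not Detected (extra) |
|---|---|---|---|
| 10 | log10(9) = 0.954 | 0.699 (0.255) | 0 (0.954) |
| 20 | log10(19) = 1.279 | 1.000 (0.279) | 0 (1.279) |

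From an illustrative baseline of exactly 1,000 IU/mL (3.0 log10), a Not Detected nadir is a change of -3.00 under the SAP. Under 10.2 it is 0.954 − 3 = -2.05 or 1.279 − 3 = -1.72. One such subject among 6 moves the cohort mean by 0.954/6 = 0.16 or 1.279/6 = 0.21 log10.

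**The case against.** The SAP may refine the protocol's data handling, since the protocol defers analysis detail to it. That is right, so the departure itself is no fault; the fault is that 6.8.1, which records even the renaming of an analysis set, omits it.

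The strongest objection concerns the order. SAP 6.1 words the log rule for data that use the LOD. Within the LOD branch alone no reversal occurs: with LOD < 1, Detected and Not Detected tie, and with LOD > 1 the order is correct or tied. The reversal needs the LLOQ/2 value for Detected to meet the LOD-based value for Not Detected. This stands as a limit: a reader might infer that the SAP will rank a deeper response as a smaller one, and the documents do not support that without knowing the assay limits and how the log rule is applied. It does not remove the problem. The SAP sends Not Detected results below the LLOQ to zero as well, so they need a log value. If the LOD rule supplies it, the reversal is possible; if it does not, no log value is defined.

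A reader might also infer that the SAP inflates the HBV DNA effect. The documents do not show that. Larger here means only larger than under 10.2. Giving undetected virus a lower value than a detected result is a defensible convention, and nothing in the documents says which number is nearer the truth.

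A reader might further infer that an LOD of 0.1 or 0.01 becomes zero and has no log. Literal subtraction gives that, but the SAP's step from 1 to 0.9 suggests moving to the next decimal place. The text is unclear on this, not demonstrably wrong.

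The consequences are bounded. The endpoints are secondary and descriptive, with no hypotheses. Medians and quartiles accompany means, listings show reported values, and active and placebo share the rule. HBsAg loss is defined by results below the LLOQ, so imputation does not touch it.

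**Conclusion.** The point holds in a limited form. Without any assumption about assays, SAP 6.1 departs from protocol 10.2 and does not say so in 6.8.1, Not Detected has different meanings on the raw and log scales, and LOD = 1 has no log rule.

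The rest is conditional. The reversal of order (0.20 log10 at an assumed LOD = LLOQ = 0.05) depends on the LOD lying close to the LLOQ and on the log rule being applied to an assay that also reports results below the LLOQ. The Part D HBV DNA difference from 10.2 is 0.95 to 1.28 log10 per Not Detected nadir at assumed limits of 10 to 20 IU/mL. It arises only in subjects below the limit, and their number is unknown. The finding is that the convention is undeclared and not coherent, and that it can change these two endpoints by an amount worth reporting; bias is not shown. It should be corrected.

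**What to change.** In SAP 6.1, state the LLOQ and LOD of each virology assay and use one ordered rule on both scales. A Detected result below the limit becomes LLOQ/2, and a Not Detected result becomes the smaller of LOD/2 and LLOQ/4. If only one limit is reported, use half and a quarter of it. The log value is then simply log10 of the raw value; it is always defined, and Not Detected is always below Detected.

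List the departure from 10.2 in SAP 6.8.1. Report the number of below-limit nadirs per cohort. Repeat the nadir summaries under protocol 10.2 as a sensitivity analysis, with a stated fallback where the limit minus one digit is zero (a literal reading of 10.2 turns <0.1 into 0.0). Applying 10.2 throughout as the main rule would meet that same problem and would not separate Detected from Not Detected.

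The cost is wording and a little programming. Some reported maximum reductions change. For HBV DNA, Not Detected becomes 2.5 (0.40 log10) at an assumed LLOQ = LOD = 10, and 5 (0.70) at LLOQ 20 with LOD 10, so those reductions shrink by 0.40 and 0.70 against the current SAP. They would still exceed those under 10.2, by 0.954 − 0.398 = 0.56 and 1.279 − 0.699 = 0.58, which is why the declaration and the sensitivity analysis are needed. For HBsAg at LLOQ 0.05, Not Detected becomes 0.0125 (-1.90) for LODs of 0.03 to 0.05, so some of those reductions grow.
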